## 3. Aim

#### 3.1 Hypothesis

The sypmtome gingival bleeding in patients suffering from VWD type 2 and 3 is not primarily due to VWD but due to inflammatory periodontal diseases (gingivitis, periodontitis).

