#### 3.2 Aim of the study,

assessment whether in patients suffering from VWD type 2 and 3 the regularly occuring symptome gingival bleeding is caused by the impaired coagulation due to VWD or due to inflammatory periodontal diseases (gingivitis, periodontitis).

If patients are diagnosed with gingivitis or periodontitis patients who want so may have periodontal treatment at the Dept. of Periodontology.

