# 5.2 Controls

For each case (VWD) a respective hematologically healthy control was recruited from the gingivitis and periodontitis patients of the Department of Periodontology, Center for Dentistry and Oral Medicine (Carolinum), Johann Wolfgang Goethe-University Frankfurt/Main. Each control was matched to one of the respective cases for sex, age (±5 years), self-reported smoking status (current smoker/non-smoker), number of

[name] & [name] (143/15: Version 2: 27.05.2015)

remaining teeth (±2 teeth), and periodontal diagnosis (gingivitis, chronic or aggressive periodontitis).

Smoking may interfere with gingival bleeding [11, 12]. Thus, all participants were asked about current and past cigarette smoking habits. Patients who reported smoking or had quit smoking for less than five years were classified as smokers [13]. Additionally the amount of carbon monoxide (CO) in exhaled air was measured using a Smokerlyzer® (Bedfont Smokerlyzer EC50-Micro; Bedfont Scientific Ltd, Rochester, Great Britain).

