# 5.7 Statistical analysis

The individual patient was used as statistical unit. All analyses were performed on patient level. BOP was defined as the main outcome variable and GBI as secondary outcome variable. All other parameters were control variables.

For all individuals, cigarette pack years were calculated. Group frequencies (VWD, control) were expressed for sex, current smoking. Group means and standard deviations were calculated for GBI, BOP, age, number of remaining teeth, pack years, CO, PCR, Body weight, VWF:Ag, VWF:RCO, FVIII:C, Hb1c. Further, for each individual the following variables were calculated to describe the periodontal status:

- Mean±standard deviation of PPD and PAL-V
- Percentage of PPD < 4 mm, 4 to 6.8 mm, ≥ 7 mm
- Sum of all PPD (Wohlfeil et al. 2009), i.e. the sum the PPD measured at all sites within a patient
- Sum of all PPD with BOP (Wohlfeil et al. 2009), i.e. the sum the PPD measured at all sites exhibiting BOP within a patient
- Periodontal inflamed surface area (PISA) [20, 21]. For each patient PPD were entered into an Excel sheet that can be downloaded freely (http://www.parsprototo.info/pisa.html).

From these group means and standard deviations were calculated. Comparisons between groups for dichotomous parameters were made by  $\chi^2$  or Fisher's exact test and for all other parameters by Mann-Whitney-U test. A post-hoc analysis was performed to estimate the test power that would be required to find a clinically relevant inter-group difference ( $\delta$ ) of 5.5% for BOP and GBI index with a type 1 error ( $\alpha$ ) of 0.05 for the actual sample size.

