Using stepwise linear backward multiple regression analysis, factors should be identified that influenced BOP and GBI. The following independent variables were entered into the model for BOP: group (VWD/control), VWD type 2 or 3, sex, age, body weight, HbA1c, PCR, CO, aMMP-8, number of remaining teeth, PISA. The following independent variables were entered into the model for GBI: group (VWD/control), VWD type 2 or 3, sex, age, body weight, HbA1c, PCR, CO, aMMP-8, number of remaining teeth, PISA. Due to the fact that mean PPD is mathematically coupled to sum of PPD, sum of PPD with BOP, and PISA these 4 variables were not entered into the regression model at the same time. PISA provides the best representation of the subgingival inflamed area. Thus, PISA was chosen for the final model. The following parameters were described by dummy variables: group (control = 0, VWD = 1), sex (male = 0, female = 1), smoking status (never and former smoker = 0, current smoker = 1). All factors with p < 0.05 were kept in the models. For statistical analysis a PC program was used (SystatTM for Windows Version 13, Systat Inc., Evanston, USA).

[name] & [name] (143/15: Version 2: 27.05.2015)

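### The claim that gingival bleeding in VWD patients is due to periodontal inflammation has no VWD-specific estimate, because the regression fits one common slope to cases and controls together

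*Combined protocol and SAP*

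**What the plan says.** Section 3.1 states that gingival bleeding in type 2 and 3 VWD "is not primarily due to VWD but due to inflammatory periodontal diseases". Section 3.2 sets the aim in the same terms: whether the symptom "is caused by the impaired coagulation due to VWD or due to inflammatory periodontal diseases (gingivitis, periodontitis". Both statements are about VWD patients, and both have two halves: VWD is not the main cause, and inflammation is.

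Section 5.2 draws controls from gingivitis and periodontitis patients and matches them on sex, age, smoking, number of teeth "and periodontal diagnosis (gingivitis, chronic or aggressive periodontitis"). Section 5.6 assigns every participant to a diagnosis, and the list starts at gingivitis, with no periodontally healthy category.

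Section 5.7 plans descriptive statistics, tests between VWD and controls, a post-hoc power estimate for the group difference, and then the regression: "Using stepwise linear backward multiple regression analysis, factors should be identified that influenced BOP and GBI". The predictors for both outcomes are "group (VWD/control), VWD type 2 or 3, sex, age, body weight, HbA1c, PCR, CO, aMMP-8, number of remaining teeth, PISA", with the coding "group (control = 0, VWD = 1"). The section lists no product of group with PCR, aMMP-8 or PISA, no fit or correlation within VWD patients, and no slope by group.

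**The concern.** The between-group tests speak to the first half of the hypothesis: does VWD add bleeding at a given periodontal diagnosis? Matching on diagnosis is designed to remove differences in periodontal disease between the groups, so those tests say little about inflammation as a cause. With no periodontally healthy category, there is no diseased-versus-healthy contrast among VWD patients either. The second half therefore rests on the regression.

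A retained PCR, aMMP-8 or PISA term shows that the marker goes with bleeding in the pooled sample. Section 2.1 already treats gingival bleeding as a leading symptom of gingivitis and untreated periodontal disease, so an association among controls is expected in advance. The common slope does not tell the reader whether the association also holds in VWD patients, or how strong it is there. At stake is a statement about cause in VWD patients that rests on a coefficient partly, and possibly mainly, supplied by patients without VWD.

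**Working it through.** **The plan's own figure.** The documents give no figure for the inflammation-bleeding association. The only calculation, in section 5.3, is for a group difference of 5.5 percentage points with 31 per group. It states no SD. It is consistent with an SD of about 7.6 to 7.7 two-sided: n = 2 x (1.960 + 0.842)² x 7.7² / 5.5² = 15.70 x 59.29 / 30.25 = 30.8, so 31 per group. At that SD, the 24 per group actually analysed give about 69% to 71% power. This concerns the group difference only.

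**What the model estimates.** With group G (0/1) and marker M, the planned structure is BOP = a + b·G + c·M + other main effects. G, and likewise the VWD type term, moves the intercept; c is the same in both groups. With equal group sizes and equal marker spread, c is the average of the two groups' slopes: c = (24 x slope in VWD + 24 x slope in controls) / 48. If the VWD slope is 0 and the standardised control slope is r, then c = r/2.

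**How often that average is significant.** Inputs: 24 + 24 patients (section 5.3) and the p < 0.05 retention rule (section 5.7). The correlations are assumptions, shown as a range, because the documents give none. There were 4,000 simulated studies per row, and 1,500 for backward selection from 11 predictors.

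| Control r (VWD r = 0) | Mean common slope | Common slope significant | Marker kept by backward selection | VWD-only test significant | Group x marker test significant |
|---|---|---|---|---|---|
| 0.3 | 0.15 | 17% | 19% | 5% | 17% |
| 0.4 | 0.20 | 27% | 29% | 5% | 26% |
| 0.5 | 0.25 | 39% | 41% | 5% | 41% |
| 0.6 | 0.30 | 54% | 55% | 5% | 56% |
| 0.7 | 0.35 | 67% | 68% | 6% | 72% |
| 0.8 | 0.40 | 79% | 81% | 5% | 88% |

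Repeat runs differed by a few percentage points (39% to 43% for the common slope at r = 0.5; up to 58% for the interaction at r = 0.6).

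Hand check at r = 0.6: the average residual variance around the common slope is 1 - r²/4 = 0.91, so SE ≈ √(0.91/48) = 0.138. Then 0.30/0.138 = 2.18 and Φ(2.18 - 2.01) ≈ 0.57. This is slightly above the simulated 54%, because it ignores chance differences in marker spread between the groups.

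**What 24 VWD patients can show.** If the association is real in VWD, an unadjusted VWD-only test has power of about 31% at r = 0.3, 51% at 0.4, 72% to 73% at 0.5 and 90% at 0.6. For 80% power, r must be about tanh((1.960 + 0.842)/√21) = tanh(0.611) = 0.545. An observed r of 0.5 has a 95% interval of tanh(0.549 ± 1.96/√21) = tanh(0.549 ± 0.428), that is 0.12 to 0.75. Adding eight unrelated covariates, an assumed stand-in for a fully adjusted model, lowers power to 20%, 32% and 54% at r = 0.3, 0.4 and 0.5. This favours a small model.

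**Which marker.** The plan does not give the PISA formula. If PISA counts surface at bleeding sites, it is partly built from BOP. A proxy on that assumption (share of bleeding sites x mean PPD x teeth, with bleeding independent of PPD) correlates about 0.93 with BOP by construction. PCR does not share this problem.

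**The case against.** The strongest reply is that the design already answers the question by elimination: if impaired coagulation were the main cause, VWD patients should bleed more than controls with the same diagnosis, and the Mann-Whitney test and the group term look for exactly that. This stands for the first half of the hypothesis. It does not reach the second. A non-significant difference with 24 per group does not show equality, and even true equality would not show that bleeding tracks inflammation within VWD patients.

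Second, a correlation of exactly zero in VWD beside 0.3 to 0.8 in controls is an assumption, and nothing in the documents suggests that VWD abolishes the usual association. This also stands. The simulation shows what the model cannot distinguish, not what is likely.

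Third, a VWD-specific slope would not separate the two causes. Impaired coagulation could amplify bleeding at inflamed sites and so produce a positive, or even steeper, slope. That is correct and limits what the added analysis may claim. For the same reason, a flat slope in VWD should not be read as the signature of a coagulation cause; the documents do not support that inference.

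Fourth, precision is poor, especially for the interaction. That stands too, and it is a reason to report intervals rather than rely on tests.

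A reader might also infer that VWD patients are not analysed at all. They are: they form half of the regression sample, and VWD type is among the predictors. What is missing is an estimate specific to them.

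**Conclusion.** The point holds in this form: the plan yields no VWD-specific estimate of the link between inflammation and bleeding, although the second half of its hypothesis needs one. The structural part follows from the listed predictors and coding and depends on no assumed value. The size does: with zero association in VWD and correlations of 0.3 to 0.8 in controls, the common slope is significant in about 17% to 79% of simulated studies of 24 + 24 patients, against about 5% for a VWD-only test.

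A reader might go further and conclude that the pooled slope was in fact driven by the controls, or that the hypothesis is wrong. The documents report no correlations or slopes, so neither follows. The group comparison is untouched. The change is worth making, because it bears directly on how the conclusion may be worded.

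**What to change.** In section 5.7, keep the planned analyses and add the following.

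1. **Main addition.** Outside the stepwise selection, fit BOP, and separately GBI, on group, PCR and group x PCR. Report the slope within the 24 VWD patients and the slope difference, each with a 95% interval, whatever the interaction p-value. If mean PPD is wanted as a second marker, fit it in its own model without PISA, in line with the section's rule on coupled variables.
2. **Supportive analysis.** From the six-sites-per-tooth records, compute for each patient the BOP percentage at sites with plaque minus that at sites without. Use only patients who have both kinds of site, state how many contribute, and summarise by group with an interval. Each patient gives one value, so this respects "All analyses were performed on patient level". Plaque is preferable to a 4 mm depth cut, because gingivitis is defined in section 5.6 by PPD below 3.6 mm and those patients would have no deep sites.
3. **Stated limits.** Say that the estimates are imprecise: VWD-only power is about 31%, 51% and 73% at r = 0.3, 0.4 and 0.5, and interaction power about 17% to 58% for control r of 0.3 to 0.6 against 0 in VWD. Say also that a non-significant interaction does not show equal slopes, and that a positive VWD slope is a cross-sectional association that does not exclude a contribution from impaired coagulation.
4. **Conclusion.** Do not attribute bleeding in VWD patients to inflammatory periodontal disease on the pooled slope alone. Word the conclusion from the VWD-specific interval together with the group difference and its interval.

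Section 5.3 already reports final recruitment. If outcome data had been seen before these analyses are added, label them as added afterwards.

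Cost: analysis work and wording, with no new data. The downside is wide intervals at n = 24.

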## Inclusion criteria:

- Age between 18 and 80 years,
- Written informed consent,
- Formerly diagnosed type 2 and 3 VWD (according to VWF multimer analysis and VWF:RCo < 30 %)

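### 'Group' and 'VWD type 2 or 3' compete in the same backward elimination, so the presence or absence of 'group' in the final model cannot be read as the adjusted VWD effect

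*Combined protocol and SAP*

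**What the plan says.** Section 5.7 of the combined protocol and SAP specifies one regression per bleeding outcome. For BOP it states: "The following independent variables were entered into the model for BOP: group (VWD/control), VWD type 2 or 3, sex, age, body weight". For GBI it repeats the list: "The following independent variables were entered into the model for GBI: group (VWD/control), VWD type 2 or 3, sex, age, body weight". Each list has 11 candidates.

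The purpose and the selection method are given as: "Using stepwise linear backward multiple regression analysis, factors should be identified that influenced BOP and GBI". The retention rule is: "All factors with p < 0.05 were kept in the models". No term is exempt from it, and no joint test of 'group' and 'type' is described.

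Coding is given for three variables only: "group (control = 0, VWD = 1), sex (male = 0, female = 1), smoking status (never and former smoker = 0, current smoker = 1". VWD type is not among them, and nothing says what value a control takes on it.

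The inclusion criteria in section 5.1 define cases as "Formerly diagnosed type 2 and 3 VWD". Section 5.2 says of the other arm: "For each case (VWD) a respective hematologically healthy control was recruited". So every case has a type and no control has one.

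**The concern.** Type is nested in group: knowing a participant's type tells you the group. When both are offered to backward elimination as if they were separate factors, they compete for the same signal, and the coefficient of 'group' no longer has a fixed meaning.

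Section 3.2 asks whether gingival bleeding comes from VWD or from periodontal inflammation. The regression is the only covariate-adjusted analysis of that question, and 'group' is the term a reader will look for. If it is absent from the final model, the reader cannot tell whether VWD showed no adjusted association or whether the association is now carried by 'type'. If it is present, the reader cannot tell which contrast it estimates without knowing the coding.

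Section 5.7 already accepts the principle for other variables: it does not enter mathematically coupled pocket-depth measures together. It does not apply the same care to the exposure.

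**Working it through.** **Inputs from the documents.** 24 cases and 24 controls analysed, and a 5.5-point target difference with alpha 0.05 and 80% power (5.3); 11 candidates, elimination at p < 0.05 (5.7). **Not in the documents:** the SD, the coding of type, and the number *k* of type 3 cases.

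**Step 1: an SD for illustration.** The planned 31 per group cannot be reproduced, because no SD is given. Solving backwards with a two-sided normal formula: SD = 5.5 × √(31/2) / (1.960 + 0.842) = 7.7. A t-based calculation gives 7.6, and a one-sided test would give 8.7. I use 7.6 as an assumption.

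**Step 2: what 'group' means under each coding.** Let τ2 and τ3 be the type 2 and type 3 differences from control.

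- *Group plus a dummy for each type:* group = type 2 + type 3, so the four columns (with the intercept) have rank 3. The terms are exactly redundant.
- *Type missing for controls:* listwise deletion removes all 24 controls, and 'group' cannot be estimated.
- *One numeric type variable:* estimable, as in the table. For scores 0/a/b, the variance inflation factor (VIF) is 1 + 12m² / [(b−a)² k(24−k)/24], where m is the mean score in cases. Example, 0/2/3 with k = 2: m = 50/24 = 2.083, so VIF = 1 + 52.08/1.833 = 29.4, and the standard error of 'group' is multiplied by √29.4 = 5.4.

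| Score (control / type 2 / type 3) | 'Group' estimates | VIF, k = 1 | k = 2 | k = 5 |
|---|---|---|---|---|
| 0/2/3 | 3τ2 − 2τ3 | 53.2 | 29.4 | 15.8 |
| 0/1/2 | 2τ2 − τ3 | 14.6 | 8.7 | 5.4 |
| 0/0/1 (type 3 dummy) | τ2 | 1.02 | 1.05 | 1.13 |
| 0/1/0 (type 2 dummy) | τ3 | 12.5 | 6.5 | 2.9 |

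The second column follows from solving β + aγ = τ2 and β + bγ = τ3 for the 'group' coefficient β, where γ is the coefficient of type. Only when τ2 = τ3 do all rows estimate the same quantity. With τ2 = 5.5 and τ3 = 11, 'group' estimates 2(5.5) − 11 = 0 under 0/1/2 coding, although both types differ from control.

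**Step 3: backward elimination, simulated.** Effect 5.5 points in both types, SD 7.6, nine independent noise covariates, k = 1, 2 or 5, at least 1,500 runs per setting (Monte Carlo error about 1 point).

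| Type entered as | 'Group' dropped, 'type' kept |
|---|---|
| 0/2/3 | 27–31% |
| 0/1/2 | 21–27% |
| type 3 dummy | 2–4% |

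Two baselines belong beside these. Without type in the list, 'group' is still dropped in about 30–31% of runs, from limited power alone. Some VWD term survives in about 71–73% of runs with type entered, against 69–70% without.

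**Step 4: sensitivity.** With 6 type 3 cases (SD 7.66), 'group' is dropped as follows:

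| Effect, type 2 / type 3 | No type | 0/1/2 | 0/2/3 | Type 3 dummy | Type 2 dummy |
|---|---|---|---|---|---|
| 5.5 / 5.5 | 32% | 47–48% | 54% | 33% | 42% |
| 8 / 8 | 6% | 27% | 37% | 8% | 17% |
| 5.5 / 11 | 16% | 76% | 75% | 31% | 11% |

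**The case against.** The strongest reply is that the VWD signal is relocated and not lost. When 'group' goes, a variable named VWD type usually stays, and the survival rates in step 3 bear this out. That stands.

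A reader might infer more: that the plan tends to hide a real VWD effect, and that losing 'group' would be taken as confirming the hypothesis in section 3.1. The documents do not support this. No section makes the absence of 'group' the criterion for the hypothesis, and losing both terms is no more frequent than losing 'group' from a model without type (28–29% against 32% with 6 type 3 cases and equal effects). It would be a false negative only if someone read the missing 'group' term as no VWD effect while ignoring a retained 'type' term.

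Three further replies also stand in part.

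- All the estimable codings fit the same three-group model, so a high VIF reflects parametrisation and not failed estimation. Group plus a type 3 dummy is a legitimate model once labelled. But the plan does not label it, and term-by-term elimination depends on the parametrisation.
- The large figures belong to ordinal coding, which the plan does not state. With a type 3 dummy and equal effects, extra dropping of 'group' is small.
- The group comparison of BOP and GBI by Mann-Whitney U test in section 5.7 does not use these terms and is untouched.

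**Conclusion.** The defect is real and lies in the covariate list itself, not only in missing detail: with both terms entered, no coding leaves 'group' as an ordinary VWD-versus-control effect unless the two types have equal effects. Selection can then assign a VWD effect to either term. The consequence is misattribution and a 'group' result that cannot be interpreted.

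The nesting and the algebra rest on the documents alone. The size does not. The 21–31% under ordinal coding and 2–4% with a type 3 dummy depend on an assumed SD, an assumed type 3 count, an unstated coding and covariates treated as pure noise, whereas plaque and inflamed surface area would be expected to relate to bleeding. They are illustrations. The point should be corrected, but it does not undermine the unadjusted comparison.

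**What to change.** 1. Remove 'VWD type 2 or 3' from the BOP and GBI models that contain 'group'. Keep 'group' in both whatever its p-value, and report its adjusted coefficient with a 95% interval.
2. Examine type in one separate exploratory model per outcome, with two dummies (type 2 versus control, type 3 versus control) replacing 'group'. Exempt both from elimination, and report each with a 95% interval and a joint 2-df test.

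The exemption matters. When the two dummies went through the p < 0.05 rule in the simulation, only one survived in about 40–58% of runs, which merges the other type with the controls and recreates the problem.

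The cost is two edited covariate lists, a changed retention rule and one extra model per outcome; no new data are needed. The downside is an imprecise type 3 estimate. Under the assumed SD and ignoring covariates, the 95% half-width is about 1.96 × 7.6 × √(1/k + 1/24): roughly 11 points with 2 type 3 patients and 7 with 5. Hence the exploratory label.

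### The BOP regression adjusts for PISA without asking whether PISA contains BOP; if it does, the VWD coefficient can be biased in either direction.

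*Combined protocol and SAP*

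**What the plan says.** All of the following is in section 5.7 of the combined protocol and SAP, unless another section is named.

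- BOP is the main outcome. Section 5.6 defines it per patient as the percentage of sites that bleed.
- The regression list opens with "The following independent variables were entered into the model for BOP: group (VWD/control), VWD type 2 or 3" and ends with PISA. Selection is backward: "All factors with p < 0.05 were kept in the models".
- Coupling is raised once: "Due to the fact that mean PPD is mathematically coupled to sum of PPD, sum of PPD with BOP, and PISA". For that reason the four measures are not entered together. The choice among them follows: "PISA provides the best representation of the subgingival inflamed area. Thus, PISA was chosen for the final model".
- On how PISA is built, the plan says only "For each patient PPD were entered into an Excel sheet that can be downloaded freely", with an external link and two citations.
- One of the four candidates does use the outcome by definition. The bleeding-site depth sum is "the sum the PPD measured at all sites exhibiting BOP within a patient".
- Outside the regression, groups are compared on BOP "for all other parameters by Mann-Whitney-U test", without adjustment.

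**The concern.** Section 3.2 asks whether gingival bleeding in type 2 and 3 VWD comes from the clotting defect or from periodontal inflammation. The regression is the only planned analysis that weighs the two together, so its group coefficient bears directly on that question.

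The plan checks whether predictors overlap with one another, but not whether a predictor overlaps with the outcome. If PISA counts pocket surface only where a site bleeds, a patient who bleeds more has a higher PISA with identical pockets. Holding PISA fixed then holds part of the outcome fixed. Some of a real VWD effect would be credited to periodontal inflammation, or, if pocket area differs between groups, an effect could appear where there is none.

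Matching does not guarantee balanced pocket area. Section 5.1 speaks of matching on severity, but the operative rule in section 5.2 uses only three diagnoses (gingivitis, chronic periodontitis, aggressive periodontitis). Section 5.6 divides chronic periodontitis into four classes of extent and depth, and these are not matched.

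**Working it through.** **Inputs from section 5.3.** 31 per group planned, difference 5.5 points, alpha 0.05, power 80%, 24 per group analysed. No SD and no sidedness are given, so the planned 62 can be back-solved but not reproduced.

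- Two-sided t-test: power 80% at 31 per group implies SD 7.6. With 24 per group, power is then 69%.
- Normal formula: SD = 5.5 / [(1.96 + 0.84) x sqrt(2/31)] = 7.73 two-sided; one-sided it is 8.71.

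**Assumptions, not in the documents.** BOP enters PISA; control BOP 20%; SD 7.6; PISA = pocket area x BOP share x 10% lognormal noise; pocket area lognormal and unrelated to BOP.

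**Mechanism.** With equal pocket area and a true effect of 5.5, mean BOP is 25.5% in cases and 20% in controls. PISA is then 25.5/20 = 1.275 times as high in cases, with no difference in pockets. Other area ratios give these case-to-control PISA ratios:

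- Control area 25% larger: 1.275/1.25 = 1.02, so PISA is almost level.
- Control area 50% larger: 1.275/1.5 = 0.85.
- Control area 20% smaller: 1.275/0.8 = 1.59.
- True effect 0, control area 25% larger: 1/1.25 = 0.80.

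**Simulation.** 24 per group, 3,000 runs per setting, BOP regressed on group and PISA. Mean group coefficient, by coefficient of variation (CV) of pocket area:

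| Control area | True effect | CV 10% | 20% | 40% | 60% | 100% |
|---|---|---|---|---|---|---|
| equal | 5.5 | 0.9 | 1.8 | 3.5 | 4.3 | 4.9 |
| equal | 0 | 0 | 0 | 0 | 0 | 0 |
| 25% larger | 0 | +3.8 | +3.1 | +1.9 | +1.1 | +0.6 |
| 20% smaller | 5.5 | -3.1 | -1.3 | 1.7 | 3.2 | 4.5 |
| 20% smaller | 0 | -3.7 | -3.1 | -1.9 | -1.1 | not tabulated |

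- Control area 25% larger, true 5.5: the estimate is 5.1 to 5.5, because PISA is nearly level.
- Control area 50% larger, true 5.5: the estimate is 8.4 falling to 5.9, an overstatement.
- False positives in the third row: 99, 72, 19, 9 and 6%.
- Bleeding-free pocket measure in place of PISA: 5.4 to 5.6, or 0 with 5 to 6% false positives, in every setting.

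**Checks under other assumptions.**

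- Pocket area mean 1200 mm2 and SD 300, SD of BOP 7.73, groups balanced: a true 5.5 becomes 2.0, with p < 0.05 in 29% of runs against 67% for a bleeding-free measure. Over area SD 100 to 600 and control BOP 12 to 30%, the coefficient runs from about 0.2 to 4.5.
- BOP truly correlated 0.4 with log pocket area: the PISA model gives 0.5 to 4.8 for a true 5.5 and -1.6 to +1.6 for a true 0. The bleeding-free model gives 5.4 to 5.5 and -0.1 to 0.0.
- Site-level data, with summed depth at bleeding sites standing in for PISA and between-patient PPD SD 0.3 mm: a true 5.5 becomes 0.9, 4.6 or -3.1 when control depth is equal, 0.5 mm deeper or 0.5 mm shallower. With mean PPD instead, the estimates are 5.3 to 5.5 for a true 5.5 and -0.1 to +0.1 for a true 0, over between-patient SDs of 0.3 and 0.8 mm.

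**The case against.** **The premise is not in the text.** Pocket depth is the only PISA input named, and the two citations given for PISA fall beyond the end of the reference list as supplied. This stands. A reader might infer that the plan demonstrably regresses BOP on itself; the documents do not show that. They show that the overlap was not considered and that the inputs are not stated.

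**The bleeding-site depth sum proves nothing by itself.** It never enters the final model, and the plan gives a separate reason for choosing PISA. This also stands. Its only relevance is that a candidate built from the outcome is discussed with no remark on that fact.

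**The direction cannot be read from the PISA group means.** It is tempting to say that higher PISA in cases means a coefficient biased downward. In a model with group and PISA only, the adjusted coefficient equals the raw difference minus the PISA slope times the difference in mean PISA. That rule describes the shift from the unadjusted coefficient. It can fail as a statement of bias when BOP depends on pocket area: in one setting PISA was lower in cases by 37, yet the PISA-adjusted value was 4.6 against a true 5.5 (unadjusted 2.5). With further covariates in the model, the identity in raw differences no longer holds; checks missed by about 0.3 to 3 points on average.

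**Mean PPD is not a full substitute.** The simulations that favour a bleeding-free measure let no inflammation differ between groups. When an assumed 0.5 SD difference in inflammation was added (correlation 0.6 with BOP), adjusting for pocket area alone gave 7.7 to 7.9 or 3.3 for a true 5.5. Adding a PCR-like covariate brought this to about 6.6 or 4.5. Residual confounding is therefore a real cost of the change.

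**The regression is exploratory.** True, and the unadjusted group comparison is unaffected. But that comparison does not adjust for pocket depth, so it cannot replace the regression on the question in section 3.2.

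**Conclusion.** The point holds conditionally. The plan adjusts its main outcome for a measure whose inputs it does not fully state, after checking overlap only among predictors. If BOP enters PISA, the group coefficient can be biased. With balanced pocket area, a true effect is pulled toward zero and a null effect is not biased. With unbalanced area, the bias can go either way and can arise with no VWD effect. If PISA is built from depth alone, this problem is absent.

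A reader might infer that the coupling always favours the study hypothesis, or that the Mann-Whitney result for BOP is compromised. Neither follows: the first needs balanced pocket area, and PISA plays no part in the second.

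The sizes shown rest on a two-sided test, SD 7.6, baseline BOP 20% and assumed spreads of pocket area, and are illustrative only. The documents give neither the size nor the direction for this study. It should be fixed because the remedy is cheap and the regression carries the study's question. Confidence is medium, because the key condition is unconfirmed.

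**What to change.** 1. In section 5.7, state exactly what enters PISA, and in particular whether BOP does.
2. Make the main BOP model the one with mean PPD in place of PISA. Mean PPD is already calculated and contains no bleeding. Keep PCR and aMMP-8 in it as inflammation covariates.
3. Keep group in that model whatever its p-value, and report its coefficient with a 95% CI.
4. Show the PISA model only as a sensitivity analysis, labelled as coupled to the outcome if BOP enters it. Beside it, give the group coefficient from the same model with PISA left out. Do not infer the direction of bias from raw differences in PISA.

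**Cost.** One defining sentence, one variable exchanged and one extra fit; no new data. R-squared will be lower. Mean PPD does not separate inflamed from quiet pockets, so confounding by inflammation may remain. If pocket depth differs between groups, precision falls: with control pocket area 25% larger, simulated power dropped from about 68% to 57% at CV 20% and to 35% at CV 10%. If PISA proves to be depth-only, little is lost.
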